7.2.2. Graded Laboratory Values

The Gilead Grading Scale for Severity of Adverse Events and Laboratory Abnormalities will be used for assigning toxicity grades (0 to 4) to laboratory results. Grade 0 includes all values that do not meet the criteria for an abnormality of at least Grade 1. Some laboratory tests have criteria for both increased and decreased levels.

Toxicity grading will be presented in listings of laboratory data. No summary tables for toxicity grading will be produced due to the effects of liver transplantation on laboratory values in the immediate post-operative period.

7.3. Body Weight, Height, BMI, and Vital Signs

Vital signs (systolic and diastolic blood pressure [mmHg] and pulse [bpm]) at each visit will be summarized for the Safety Analysis Set using descriptive statistics (n, mean, SD, median, Q1, Q3, minimum, and maximum) for the SOF/VEL 4 Week group. The baseline value will be defined as the last available value collected on or prior to the date of first dose of study drug. In the case of multiple values in an analysis window, data will be selected for analysis as described in Section 3.8.3 of this SAP. No inferential statistics will be generated.

A by-subject listing of height (cm), body weight (kg), BMI (kg/m²) and vital signs (systolic and diastolic blood pressure [mmHg], pulse [bpm], respiration [breaths/min], and body temperature [°C]) will be provided. Data will be sorted for each subject and visit in chronologic order.

7.4. Prior and Concomitant Medications

Medications collected at screening and during the study will be coded using the current version of the World Health Organization (WHO) Drug dictionary. The medications will be categorized as prior or concomitant using the following definitions:

- Prior medications: any medications taken and stopped prior to or on the date of first study drug administration
- Concomitant medications: any medications taken after the date of first study drug administration and up to the last dosing date of study drug

Concomitant medications (other than study drug and drugs administered to prevent rejection of the transplanted organ) will be summarized by preferred drug name using the number and percentage of subjects for the SOF/VEL 4 Week group. A subject reporting the same medication for a preferred drug name more than once will be counted once only per subject. The summary of concomitant medications will be ordered by descending frequency of preferred drug name. For preferred drug names with the same frequency, sorting will be done alphabetically.

Summaries will be based on the Safety Analysis Set. No inferential statistics will be generated.

For purposes of analysis, any medication with a stop date that is on or prior to the initial study drug dosing date or start date that is after the last study drug dosing date will be excluded from a concomitant medication summary. If a partial stop date is entered, any medication with the month and year (if day is missing) or year (if day and month are missing) prior to the initial study drug start date will be excluded from the concomitant medication summary. If a partial start date is entered, then any medication with the month and year (if day is missing) or year (if day and month are missing) after the study drug stop date will be excluded from the concomitant medication summary.

All prior and concomitant medications (other than per-protocol study drugs and drugs administered to prevent rejection of the transplanted organ) will be provided in a by-subject listing sorted by subject ID number and administration date in chronologic order.

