If the transplant is completed before noon, the subject will take their first dose that day after the transplant which will be considered Day 1. If the transplant is completed after noon, the subject will take their first dose the following morning which will be considered Day 1. The planned first dose may be delayed for up to 1 day if, in the investigators opinion, delay is in the subject's medical interest. The subject will receive 4 weeks of study drug.

On-treatment assessments starting at Day 1 will include vital signs, ECG (only at Day 28), AEs, CMs (including immunosuppressive therapy), safety laboratory tests, estimated  $Cl_{cr}$ , HCV RNA, study drug dosing adherence and urine pregnancy tests (females of childbearing potential only).

Post-treatment assessments through Post-treatment week 4 only include AEs and CMs. Weight, vital signs, and urine pregnancy tests (females of child bearing potential only) will only be done at Post-treatment week 4. Pregnancy prevention counseling will be done at Post-treatment week 1 only. Safety laboratory tests, HCV RNA and viral sequencing samples will be collected through all Post-treatment visits.

Samples for viral RNA sequencing/phenotyping will be collected starting at Day 1 and every visit thereafter.

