## 2. OBJECTIVES

The primary objectives of this study are:

- To explore the antiviral efficacy of treatment with SOF/VEL FDC therapy administered for four weeks following liver transplantation as measured by sustained virologic response 12 weeks after cessation of treatment (SVR12)
- To evaluate the safety and tolerability of SOF/VEL in HCV-infected subjects in the peri-operative and post-transplant period

The secondary objectives of this study are:

- To determine the percentage of subjects who attain SVR at 4 weeks after cessation of treatment (SVR4)
- To evaluate the proportion of subjects with virologic failure
- To assess rates of graft survival, graft function, acute rejection and immunosuppressive therapy during treatment with SOF/VEL
- To evaluate the emergence of viral resistance to SOF and VEL during treatment and after cessation of treatment
- To evaluate the kinetics of circulating HCV RNA during treatment and after cessation of treatment
- To characterize pharmacokinetics of SOF/VEL

The exploratory objectives of this study are:

PPD

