3.8. Visit Windows

3.8.1. Definition of Study Day

Study day is the day relative to the date of the first dose of study drug. Study Day 1 will be defined as the day of the first dose of study drug administration.

Study day will be calculated from the date of first dose of study drug administration and derived as follows:

- For postdose study days: Assessment Date – First Dose Date + 1
- For days prior to the first dose: Assessment Date – First Dose Date

The last dose date of study drug will be the end date for SOF/VEL on the study drug administration eCRF for the record where the “subject permanently discontinued” flag is ‘Yes’.

If there are subjects for whom the date of last study drug is unknown due to the reason that the subject was lost to follow-up and not able to be contacted, the date of last dose will be estimated using the maximum of nonmissing study drug start or stop dates, and on-treatment visit dates and laboratory collection dates (posttreatment visits and unscheduled visits are not included).

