7.5. Concomitant Immunosuppressant Medications

Immunosuppressant medications administered to prevent rejection of the transplanted organ collected at screening and during the study will be coded using the current version of the World Health Organization (WHO) Drug dictionary. Concomitant (as described in Section 7.4) immunosuppressant medications will be summarized by preferred drug name for the SOF/VEL 4 Week group for subjects in the Safety Analysis Set.

All prior and concomitant immunosuppressant medications administered to prevent rejection of the transplanted organ will be presented in a by-subject listing sorted by subject ID number and start date of administration for subjects in the safety analysis set.

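### SAP 7.4 counts a drug stopped on the first-dose date as prior, so a drug given only on Day 1, after SOF/VEL, is left out of Tables 7 and 8

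*SAP*

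**What the plan says.** SAP 7.4 sorts medications by date into two classes. The first is the one that no summary table covers: "Prior medications: any medications taken and stopped prior to or on the date of first study drug administration". The second is the one that feeds the summary tables: "Concomitant medications: any medications taken after the date of first study drug administration and up to the last dosing date of study drug".

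The same section then restates the boundary as a rule for the concomitant summary, leaving out "any medication with a stop date that is on or prior to the initial study drug dosing date". SAP 7.5 adopts the definition for anti-rejection drugs: "Concomitant (as described in Section 7.4) immunosuppressant medications will be summarized by preferred drug name". The listings are wider than the tables: "All prior and concomitant immunosuppressant medications administered to prevent rejection of the transplanted organ will be presented in a by-subject listing". SAP 7.4 plans a similar listing for all other drugs.

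SAP 3.8.1 fixes the boundary day: "Study Day 1 will be defined as the day of the first dose of study drug administration". Protocol section 2 makes the topic a secondary objective: "To assess rates of graft survival, graft function, acute rejection and immunosuppressive therapy during treatment with SOF/VEL". Protocol 8.1.5 also names changes to immunosuppression as an endpoint of interest.

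**The concern.** The first-dose date is a day of treatment, but the medication rule puts it on the pre-treatment side. A drug given once on that date, after the first SOF/VEL tablet, overlaps with study treatment and is still labelled prior. No table of prior medications is planned, so such a drug appears in no summary table.

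This matters more here than in most trials because treatment starts soon after major surgery. Day 1 is the transplant day or shortly after it, when a drug may be given for one day only. Table 8 is the only planned tabulation of immunosuppressants and the only summary that addresses that part of the secondary objective. If an agent was given on Day 1 and never again, a reader of Table 8 would conclude that it was not used during treatment.

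**Working it through.** The plan states no figure on this point. The check applies the written rule to dated records and then compares it with the other date rules in the documents.

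**Inputs.** First dose = Study Day 1 (SAP 3.8.1). Last dose = Day 28 for a full course (SAP 4.2.2.1: one tablet a day for 28 days). Planned subjects = 10 (SAP 1.3).

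**Rule as written (SAP 7.4).** Exclude from the concomitant summary if stop ≤ first-dose date, or if start > last-dose date.

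**Rule after the change.** Exclude if stop < first-dose date, or if start > last-dose date.

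| Record | As written | After the change |
|---|---|---|
| Day before first dose only | excluded | excluded |
| Pre-operative start, stopped Day 1 | excluded | included |
| Day 1 only | excluded | included |
| Day 1 to Day 2 | included | included |
| Day 1, ongoing | included | included |
| Day 2 only | included | included |
| Day 28 only | included | included |
| Started Day 29 | excluded | excluded |

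The written rule keeps a one-day record on any of Days 2 to 28 (28 − 1 = 27 days) and drops it on Day 1. The last-dose date is inside the period and the first-dose date is outside it. An invented example: transplant ends at 10:00, SOF/VEL is given at 14:00, and an immunosuppressant is given once at 20:00 the same day. Its stop date equals the first-dose date, so it is prior.

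**Comparison with the other date rules.**

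- Protocol 8.6 counts safety data from Study Day 1 onward as on treatment.
- SAP 4.2.1 computes exposure as last-dose date − first-dose date + 1, so Day 1 is a full day of exposure.
- SAP 7.1.5.1 treats an AE that starts on the first-dose date as treatment-emergent. A drug given once that day for that AE would be prior.
- The partial-date rule in SAP 7.4 drops a drug only when its stop month or year is earlier than that of the first dose. A record with an unknown stop day in the first-dose month is kept, while one known to have stopped on Day 1 is dropped.
- SAP 7.8 reports no departure from the protocol's safety analyses.

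**Where the excluded records go.** In SAP section 12, Tables 7 and 8 are the only medication-use tables, and both are limited to concomitant drugs. Listings 6.1 and 7 hold prior and concomitant records together.

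**Size.** One misclassified subject changes a drug's percentage by 1/10 = 10 points, and k subjects change it by 10k points. The documents give no value for k. It can lie anywhere from 0 (no effect) to 10. A subject counts towards k only if every record of that preferred drug name stops by Day 1, because SAP 7.4 counts each subject once per name and any later on-treatment record brings the subject back.

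**The case against.** The strongest defence is that this is a convention, stated twice and consistently. A rule based on dates alone must put the boundary day on one side, and moving it creates the opposite error: when the first dose follows surgery on the same day, a drug given in theatre and stopped before that dose really is prior. That trade-off is genuine and has to be disclosed in any revision. It does not justify the present choice, because SAP 7.4 and SAP 7.1.5.2 otherwise keep ambiguous dates in their summaries, and the other date rules count Day 1 as treatment.

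Several limiting points stand in full. With about 10 subjects, Listings 6.1 and 7 can be read record by record. No hypothesis is tested, and Tables 7 and 8 are not marked for the DMC. Protocol 7.5 says drugs related to the transplant procedure need not be recorded, so some one-day drugs may never reach the database. That does not settle the matter for immunosuppressants, since the protocol synopsis names them among the medications assessed from Day 1.

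A reader might infer three stronger claims that the documents do not support:

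- *That Day 1 is the operative day.* The protocol says "If the transplant is completed before noon, the subject will take their first dose that day after the transplant which will be considered Day 1". Surgery that finishes later in the day moves Day 1 to the next day, and the first dose may be delayed by up to one further day. No frequencies are given.
- *That the rule compromises the Day 1 PK analysis by hiding acid reducers.* The protocol does report VEL AUC reductions of 26% to 56% with omeprazole 20 mg, and Day 1 is the intensive PK day. But Table 7 carries no dates, so even a complete table could not show who took an acid reducer that day. Listing 6.1 can. The PK summaries group by route and do not use Table 7.
- *That Table 8 would show none of 10 subjects where all 10 received a drug.* This assumes that every subject received a one-day agent on Day 1 and never again, which nothing in the documents establishes.

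**Conclusion.** The point holds as a minor inconsistency in definitions. As written, SAP 7.4 and 7.5 leave out of Tables 7 and 8 any drug whose records all stop by the first-dose date, including one given after the first SOF/VEL dose. This disagrees with the treatment period used for exposure, AEs and other safety data, and it touches a secondary objective. The size is 10 percentage points per affected subject, assuming the planned 10 subjects. The number affected cannot be derived from the documents and may be zero. Nothing is lost from the listings, and no PK, SVR12 or AE result changes.

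**What to change.** In SAP 7.4:

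- Define a prior medication as one stopped before the date of first SOF/VEL dose.
- Define a concomitant medication as one stopped on or after that date, or ongoing, and started on or before the last-dose date.
- Change the exclusion sentence so that it removes only drugs with a stop date earlier than the first-dose date.

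State in SAP 7.5 that the revised definitions apply to immunosuppressants. The partial-date rule already fits the revised boundary and can stay.

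On dates alone, the new rule would count a drug stopped on Day 1 before the first dose as concomitant. Protocol 6.3 has the time of the first dose recorded. Where the drug's administration time is also recorded, classify such records by comparing the two times. Otherwise, footnote records that stop on Day 1 in Tables 7 and 8. A flag for Day 1-only drugs would not be enough, because it cannot separate pre-dose from post-dose use and misses drugs started earlier and stopped that morning.

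The cost is two definitions, one sentence, a confirming line in 7.5, and a time comparison or footnote in programming. No new data are needed.

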7.5. Concomitant Immunosuppressant Medications

Immunosuppressant medications administered to prevent rejection of the transplanted organ collected at screening and during the study will be coded using the current version of the World Health Organization (WHO) Drug dictionary. Concomitant (as described in Section 7.4) immunosuppressant medications will be summarized by preferred drug name for the SOF/VEL 4 Week group for subjects in the Safety Analysis Set.

All prior and concomitant immunosuppressant medications administered to prevent rejection of the transplanted organ will be presented in a by-subject listing sorted by subject ID number and start date of administration for subjects in the safety analysis set.

7.6. Investigator Electrocardiogram Assessment

A by-subject listing for ECG assessment results collected at screening and at the pre-surgery visit including comments regarding clinically significant abnormalities will be provided for subjects in the safety analysis set. ECGs will be listed by the nominal visit and will be presented in chronological order.

7.7. Other Safety Measures

A data listing will be provided for subjects who become pregnant during the study.

7.8. Changes From Protocol-Specified Safety Analyses

There are no deviations from the protocol-specified safety analyses.

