**Criteria for Evaluation:**

**Safety:** AEs and safety laboratory tests will be collected throughout the study (through the Post-treatment week 4 visit).

**Efficacy:** Efficacy will be evaluated using scheduled assessments of HCV RNA performed using Roche COBAS® AmpliPrep/COBAS® TaqMan® HCV Test, v. 2.0.

**Pharmacokinetics:** A single PK blood sample will be collected at each on-treatment visit for all subjects except on Days 1, 3 and 5.

All subjects will be required to participate in an intensive serial PK sub-study to be performed on Day 1. The PK of SOF (and its metabolites GS-566500 and GS-331007), and VEL will be assessed. Serial PK samples will be collected at the following time points: 0 (pre-dose), 0.5, 1, 2, 4, 8, 12 and 24 hours post-dose.

---

---

**Statistical Methods:** The primary efficacy endpoint is the percentage of subjects who achieve SVR12 (HCV RNA < lower limit of quantitation [LLOQ] 12 weeks after stopping study drug) for subjects in the Full Analysis Set (FAS).

Secondary efficacy endpoints include the percentage of subjects who attain SVR at 4 weeks after cessation of treatment (SVR4); the percentage of subjects who have HCV RNA <LLOQ at each on-treatment visit; and the percentage of subjects with virologic failure (VF, defined as HCV RNA  $\geq$  LLOQ at end of treatment or relapse during the Post-treatment follow-up period).

The primary safety endpoint is the percentage of subjects who discontinue from study drug due to an adverse event. Deaths, graft loss, and rejection episodes will also be listed or summarized, as appropriate.

Other endpoints of interest include changes to immunosuppressive therapy and the emergence of viral resistance to SOF or VEL during and after cessation of treatment, and HCV RNA levels (IU/mL) at each on-treatment visit, if relevant.

---

This study will be conducted in accordance with the guidelines of Good Clinical Practice (GCP) including archiving of essential documents.

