### **8.1.4. Safety Endpoint**

The primary safety endpoint is any AE leading to premature discontinuation of study drug. Other important safety endpoints include deaths, graft losses, and rejection episodes.

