## **8.6. Safety Analysis**

Safety will be evaluated by assessment of clinical laboratory tests, physical examinations, and vital signs measurements at various time points during the study, and by the documentation of AEs.

All safety data collected while “on treatment” (ie, on or after Study Day 1 up to 30 days after the last dose of study drug) will be summarized for subjects who receive SOF/VEL.

Safety endpoints will be summarized as the number (percentage) of subjects with events or abnormalities for categorical data or as an 8-number summary (n, mean, standard deviation, median, Q1, Q3, minimum, maximum) for continuous data.

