### **8.6.2. Adverse Events**

Clinical and laboratory adverse events will be coded using the Medical Dictionary for Regulatory Activities (MedDRA). System Organ Class (SOC), High-Level Group Term (HLGT), High-Level Term (HLT), Preferred Term (PT), and Lower-Level Term (LLT) will be attached to the clinical database.

Events will be summarized on the basis of the date of onset for the event. A treatment-emergent adverse event will be defined as any adverse event with an onset date on or after the study drug start date and no later than 30 days after permanent discontinuation of study drug or any adverse event leading to premature discontinuation of study drug.

Summaries (number and percentage of subjects) of treatment-emergent adverse events (by SOC and preferred term) will be for subjects receiving SOF/VEL provided for:

- All AEs,
- All study drug-related AEs,
- Combined Grade 2, 3 and 4 AEs,
- Combined Grade 3 and 4 AEs,
- Combined Grade 2, 3 and 4 study drug-related AEs,
- Combined Grade 3 and 4 study drug-related AEs,
- All AEs that caused permanent discontinuation from study drug,
- All AEs that caused temporary interruption of study drug,
- All SAEs (including death), and
- All study drug-related SAEs

All AEs collected during the course of the study will be presented in data listings.

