7.1.6. Summaries of Adverse Events and Deaths

A brief high-level summary of TEAEs will be provided for the SOF/VEL 4 Week group. The number and percentage of subjects who had the following: any AE; any treatment-related AE; any AE of Grade 3 or above; any treatment-related AE of Grade 3 or above; any AE of Grade 2 or above; any treatment-related AE of Grade 2 or above; any SAE; any treatment-related SAE; any AE leading to premature discontinuation of SOF/VEL; and any AE leading to interruption of SOF/VEL. All deaths (including those that are treatment-emergent and those that are not treatment-emergent) observed during the study will also be summarized and included in this table.

Adverse event summaries will provide the number and percentage of subjects with TEAEs by SOC and PT for the SOF/VEL 4 Week group based on the the Safety Analysis Set as follows:

- All AEs
- All treatment-related AEs
- AEs of Grade 3 or above
- Treatment-related AEs of Grade 3 or above
- AEs of Grade 2 or above
- Treatment-related AEs of Grade 2 or above
- All SAEs
- Treatment-Emergent Non-Serious Adverse Events Occurring in At Least 5% of Subjects

Multiple events will be counted once only per subject in each summary. Adverse events will be summarized and listed first in alphabetic order of SOC and then by PT in order of descending incidence within an SOC. In summaries by severity grade, the most severe grade will be used for those AEs that occurred more than once in an individual subject during the study.

In addition to the above summary tables, TEAEs will also be summarized for the SOF/VEL 4 Week treatment group by PT only, in order of descending incidence for:

- AEs that occurred in > 1 subject
- AEs leading to interruption of SOF/VEL
- AEs leading to premature discontinuation of SOF/VEL
- All SAEs
- All treatment-related SAEs

In addition to the by-treatment summaries described above, by-subject data listings, with a variable indicating whether the event is treatment-emergent, will be provided for the following:

- All AEs
- AEs leading to premature discontinuation of SOF/VEL
- All AEs of Grade 3 or above
- SAEs
- All Deaths
- Graft Loss

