7.1.7. Additional Analysis of Adverse Events

None

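### Rejection episodes are a protocol-named safety endpoint, but the SAP plans no output for them and declares no change, so a rejection rate is not assured

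*SAP*

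**What the plan says.** **Protocol.** Section 8.1.4, after the primary safety endpoint, states: "Other important safety endpoints include deaths, graft losses, and rejection episodes". The synopsis, under Statistical Methods, commits to reporting: "Deaths, graft loss, and rejection episodes will also be listed or summarized, as appropriate". A secondary objective in Section 2, repeated in SAP 1.1, is "To assess rates of graft survival, graft function, acute rejection and immunosuppressive therapy during treatment with SOF/VEL". Section 8.6 gives the general format: "Safety endpoints will be summarized as the number (percentage) of subjects with events or abnormalities for categorical data". Section 8.6.2 itemizes the AE summaries, with no rejection table among them, and adds: "All AEs collected during the course of the study will be presented in data listings".

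**SAP.** Section 7.1.6 says that "by-subject data listings, with a variable indicating whether the event is treatment-emergent, will be provided for the following", and then names six: all AEs, AEs leading to discontinuation, AEs of Grade 3 or above, SAEs, deaths, and graft loss. Section 7.1.7 plans no additional AE analysis. Section 7.7 adds a pregnancy listing only. Section 7.8 states "There are no deviations from the protocol-specified safety analyses".

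**AE reporting.** Protocol 7.3 requires AEs to be reported except those covered by Section 7.5. Section 7.5 keeps events clearly due to the transplant, including its direct consequences, out of AE and SAE collection. It restores reporting for events that were not an expected part of the transplant process and for events possibly or probably related to study drug. It does not mention rejection.

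**The concern.** Three endpoints are named in one sentence of the protocol. The SAP carries two of them into outputs of their own, drops the third without comment, and then declares that nothing has changed. Anyone using SAP 7.8 to check the SAP against the protocol would not be alerted.

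What is at stake is whether the secondary objective can be answered. It asks for a rate of acute rejection during treatment. As the SAP stands, that rate could come only from the general AE outputs, and what reaches those outputs depends on how the site reads the Protocol 7.5 exemption. If no rejection term appears, the reader cannot tell that none occurred from none having been reportable.

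**Working it through.** The plan gives no rejection figure to reproduce, so the check compares commitments with planned outputs and then follows the data route.

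**Step 1. Count the planned outputs (SAP 12 index, PK items excluded).**
- Tables: 1 (Table 1) + 2 (2.1, 2.2) + 26 (3 to 28) + 15 (29.1 to 29.15) + 1 (30) + 3 (31.1 to 31.3) = 48. Titled for rejection: 0.
- Listings: 26 numbers + 10 extra sub-numbers (2.2, 3.2, 5.2, 6.2, 13.2, 16.2, 16.3, 17.2, 19.2, 22.2) = 36. Titled for rejection: 0.
- By-subject listings named in SAP 7.1.6: 6. For rejection: 0.

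Many of these outputs are laboratory, vital-sign or screening displays that would never carry rejection. The informative comparison is Step 2.

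**Step 2. Set the three endpoints of Protocol 8.1.4 side by side.**

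| Endpoint | Synopsis commits to list or summarize | Own SAP output |
|---|---|---|
| Deaths | Yes | Listing 13.1, and a line in the brief AE summary (SAP 7.1.6) |
| Graft loss | Yes | Listing 13.2 |
| Rejection episodes | Yes | None |

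Two of three have an output of their own.

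**Step 3. Look for rejection elsewhere in the SAP.** In the SAP text available, the word occurs five times: once in the objectives (1.1), and four times describing drugs given to prevent it (twice in 7.4, twice in 7.5). It is never an analyzed event. Table 8 and Listing 7 report immunosuppressant drugs, not episodes.

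**Step 4. Follow the indirect route.** A rejection entered as an AE would be counted in Table 16 if treatment-emergent, and shown in Listing 8. Depending on grade and seriousness it would also appear in Table 18 and Listings 9 and 11. All five are marked for the DMC. This route works only if the episode is entered as an AE. Under Protocol 7.3 and 7.5 a site could:
- treat rejection as a direct consequence of transplantation and not report it;
- treat it as unexpected, or possibly drug-related, and report it; or
- ask the Medical Monitor, as 7.5 invites in case of doubt.

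The text does not settle which applies.

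**Step 5. Look for a separate data source.** SAP 5.1 refers to a liver transplant eCRF, but its content is not in the documents. Whether it records rejection is unknown.

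**Step 6. Size.** The documents give no rejection rate, and none is assumed. With the planned 10 subjects, one affected subject who is not recorded lowers the observed rate by 1/10 = 10 percentage points.

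**The case against.** The best defense is that the protocol never promises a dedicated rejection output. The synopsis leaves the form open, Protocol 8.1.4 names the endpoint without prescribing a display, and the itemized list in 8.6.2 has no rejection table. A rejection recorded as an AE would be listed in Listing 8 and counted with a percentage in Table 16, which could satisfy the synopsis. On that reading SAP 7.8 is not untrue. Section 7.5 does not name rejection, its only example of a direct consequence is minor (line insertion), and a site that has read 8.1.4 has good reason to report rejection. The study is small, descriptive and at about one center, and rejection is not the primary safety endpoint.

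Much of this stands. The open wording does allow a choice between listing and summary, and general AE outputs could carry the result. What it does not do is assure that result. The defense needs every rejection to be entered as an AE, and the protocol text does not secure this. Nor did the SAP regard general AE outputs as enough for deaths or graft loss, and it gives no reason to treat rejection differently.

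Three stronger readings are tempting and should be resisted. A reader might infer that the rejection data are missing; the documents show only that capture is uncertain. A reader might infer that the DMC would see no rejection events; those recorded as AEs would reach it through the starred outputs. A reader might infer that SAP 7.8 is plainly false; whether it is depends on how the synopsis sentence is read and on what was collected.

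**Conclusion.** The point holds as a gap in the plan. One of three safety endpoints named together, which also forms part of a secondary objective, has no output of its own, and the SAP declares no change. The rejection result is not assured, and a zero count from the AE outputs could not be interpreted.

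The conclusion rests on the SAP index and Section 7 text, which are unambiguous, and on Protocol 7.5 being open to a reading that exempts rejection, which is a matter of interpretation. It assumes nothing about how often rejection occurs. The primary efficacy result is unaffected. The change is worth making because it is cheap and because the objective otherwise has no assured answer.

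**What to change.** 1. In SAP 7.1.6 and the SAP 12 index, add a by-subject rejection listing parallel to Listing 13.2, and the number and percentage of subjects with at least one rejection episode in the Safety Analysis Set. State the data source.
2. Define what counts as an episode, since neither document does. One workable rule is investigator-recorded acute rejection, with biopsy confirmation shown where it was recorded. Without a definition the percentage is not reproducible.
3. Before database finalization (SAP 2.2), query the site to confirm that the recorded episodes are complete.
4. If rejection was not systematically collected, amend SAP 7.8 to say that this protocol-named endpoint is reported only through AE data, subject to the Protocol 7.5 exemption. If the SAP is already final, SAP 1 provides for recording the change in the clinical study report.

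The cost is one listing, one summary line and a short query round for about 10 subjects at about one center. If the site did apply the exemption to rejection, the query becomes retrospective collection and takes more work; step 4 is then the minimum. SAP 3.1.2 indicates that all enrolled subjects have already been dosed, so the new outputs may come too late for one or both DMC meetings, but they can still serve the final analysis if the database is not yet finalized.
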